#### *5.3.1.2 Snaith Irritability Scale (SIS)*

The SIS is a brief rating scale of irritability by self-report.[41]. The scale is composed of eight items each rated on a four-point scale. Four items are focused on inward irritability and four items are focused on outward irritability.

#### *5.3.1.3 Columbia Suicide Severity Rating Scale (CSSRS)*

The Columbia Suicide Severity Rating Scale (CSSRS) was developed in the National Institute of Mental Health Treatment of Adolescent Suicide Attempters Study to assess severity and monitor suicidal events during a treatment period [42, 43]. It can be administered by a rater following a structured interview. The interview can provide an overall assessment of suicidal ideation as well as suicidal behavior in order to generate a summary measure of suicidality. All personnel involved in this assessment will be informed of the risk indicators and local protocols for appropriate referrals.

### **5.3.2 Extended Cognitive Assessments**

#### *5.3.2.1 The Stroop Interference Test*

The Stroop Interference Test is a neuropsychological test of cognitive flexibility and resistance to interference. It involves reading words of colors (e.g. red, green blue) where the word color is written in a different color ink.

#### *5.3.2.2 The Trail Making Tests*

The Trail Making Tests are neuropsychological tests measuring visual attention and task switching.

#### *5.3.2.3 The Mini Mental State Examination (MMSE)*

The Mini Mental State Examination (MMSE) is an 11-question measure that tests five areas of cognitive function: orientation, registration, attention and calculation, recall, and language [44].

### **5.3.3 Physiotherapy Outcome Measures**

#### *5.3.3.1 Timed Up and Go (TUG)*

The timed up and go test is a measurement of mobility. It includes a number of tasks such as standing from a seating position, walking, turning, stopping, and sitting down which are all important tasks needed for a person to be independently mobile. The participant is asked to stand up from a standard chair and walk a distance of approximately 10 feet (measure as 3 meters), turn around and walk back to the chair and sit down again. The individual uses his/her usual footwear and can use any assistive walking device they normally use, such as a cane. The person is seated with his/her back to the chair, their arms resting on the arm rests, and any walking aid they may use should be in hand. Timing, using either a wristwatch with a second hand or a stop watch, begins when the individual starts to rise from the chair and ends when he/she is once again seated in the chair. The normal time required to finish the test is between 7 – 10 seconds. The TUG has been studied in HD and has been shown to predict falls in this population.

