### **5.3 Extended Assessments**

These data elements are to be collected to the extent possible on all participants at all sites.

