### **6.2 Data Analysis**

Descriptive analyses will be conducted in support of the objective of providing natural history data including cognitive, behavior, motor progression and insights into the neurobiology of HD. Individual sub-study proposals will develop data analysis plans specific to the objectives of each sub-study. Qualified researchers can apply for and obtain access to the anonymised Enroll-HD data to perform additional exploratory or data mining analyses. If necessary, investigators may request guidance for development and implementation of statistical analyses from the Enroll-HD Steering Committee.

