#### **ASSESSMENT BATTERY:**

- a. The 6-Minute Walk test.
- b. The 10m Walk test
- c. The timed "Up and Go".
- d. Physical Performance Test
- e. Rivermead Mobility Index
- f. Barthel Index
- g. Berg Balance Scale
- h. Romberg and Sharpened Romberg Test
- i. Performance Oriented Mobility Assessment
- j. Four square step test
- k. International Physical Activity Questionnaire

**ASSESSMENT DURATION:** 60-90 minutes, two visits (one week apart). This study will be coordinated by the Physiotherapy Working Group Lead Facilitators.

**METHODOLOGICAL APPROACH:** Eighty participants with Huntington's disease; 20 pre-HD (TFC 13; no clinical signs of HD); 20 Stage I HD (TFC 10-13); 20 Stage II HD (TFC 7-9); 20 Stages III and IV (TFC 0-6). Twenty participants (tested twice) in each stage of disease would be sufficient to identify an intraclass correlation coefficient of .75, as well as a Pearson's correlation of .6 (two-tailed), with a power of 80% and an alpha of .05.

**OUTCOMES:** Reliability will be assessed using the Intra class correlation coefficient. Validity will be assessed using a Pearson's or Spearman's correlation coefficient correlating functional outcome measures with UHDRS Motor score and Functional Assessment scale for each subject. Minimal Detectable Change (MDC) will be calculated as  $1.96 * \sqrt{2} * SEM$  (standard error of measurement). SEM will be estimated by taking the square root of the mean error term from a repeated measures ANOVA. The MDC can be interpreted as the magnitude of change below which there is more than a 95% chance that no real change has occurred.

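### The Timed Up and Go may be timed by a wristwatch second hand or a stopwatch, which allows avoidable and uneven reading error on a test that normally takes 7 to 10 seconds

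*Protocol*

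**What the plan says.** Protocol Section 5.3.3.1 describes the TUG and permits timing "using either a wristwatch with a second hand or a stop watch". Timing "begins when the individual starts to rise from the chair and ends when he/she is once again seated in the chair". The section also states: "The normal time required to finish the test is between 7 – 10 seconds". It sets no recording resolution and does not ask for one device to be kept across visits or sites.

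In the main study the TUG is an extended assessment. Section 5.3 says of these: "These data elements are to be collected to the extent possible on all participants at all sites". The main-study analysis in Section 6.2 is descriptive: "Descriptive analyses will be conducted in support of the objective of providing natural history data".

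The TUG is also in the battery of the physiotherapy sub-study (Section 10.1.9). For that sub-study, "Minimal Detectable Change (MDC) will be calculated as" 1.96 × √2 × SEM, and "SEM will be estimated by taking the square root of the mean error term from a repeated measures ANOVA". Section 10.1.9 names no timing device and gives no value for the SEM or the MDC of the TUG.

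**The concern.** The protocol accepts two instruments of clearly different resolution for one short measurement. A running second hand has to be read twice, at the start and at the end, and each reading is rounded. A stopwatch starts from zero and is read once, to a fraction of a second.

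Two things are at stake. First, the TUG is repeated yearly and the study's objectives include estimating rates of progression (Section 3, Objective 1a) and qualifying assessment tools and endpoints (Objective 3a). If devices differ by site or visit, so does the measurement error, and the analyst cannot tell which readings are coarse unless the device is recorded. Second, where an MDC is calculated, reading error forms part of the repeated-measures error term and can only raise the result. Section 5.1 asks sites to keep the same rater for each participant where possible, for the sake of consistency; leaving the timing device open works against that aim.

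**Working it through.** **Inputs from the protocol.** Permitted devices and normal time of 7 to 10 s (Section 5.3.3.1). MDC = 1.96 × √2 × SEM, with SEM the root of the repeated-measures error term (Section 10.1.9).

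**Inputs not in the protocol, so assumed.** The resolution at which a second hand is read, and the SEM of the TUG apart from reading error. Both are varied below.

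**The plan's own figure.** The protocol gives no figure for TUG timing error. The nearest stated number is 20 participants per stage in Section 10.1.9, for a Pearson correlation of 0.6, two-tailed alpha 0.05 and 80% power. By Fisher's z, n = ((1.960 + 0.842) / atanh(0.6))² + 3 = 19.3, rounded up to 20. It reproduces, and it does not depend on how the TUG is timed.

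**Step 1: rounding error per test.** A reading rounded to a unit u has a uniform error with SD u/√12. Two independent readings give u × √(2/12). A simulation of 2,000,000 tests with durations uniform on 7 to 10 s agrees with these values.

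| Reading | Error SD | MDC from rounding alone (× 1.96 × √2 = 2.772) |
|---|---|---|
| Second hand, both ends to the whole second | √(2/12) = 0.408 s | 1.13 s |
| Second hand, start on a tick, end to the whole second | 1/√12 = 0.289 s | 0.80 s |
| Second hand, both ends to the half second | 0.5 × √(2/12) = 0.204 s | 0.57 s |
| Stopwatch recorded to 0.1 s, one reading | 0.1/√12 = 0.029 s | 0.08 s |

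With both ends read, the second hand is therefore 0.204/0.029, or about 7, to 0.408/0.029, or about 14, times coarser than the stopwatch. Relative to the normal time, 0.408 s is 4.1% of 10 s and 5.8% of 7 s.

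**Step 2: effect on an actual MDC.** Independent error variances add, so MDC = 2.772 × √(SEM² + SD²), where SD is the rounding error. The relative increase is √(1 + SD²/SEM²) − 1.

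| Assumed SEM without rounding | MDC without rounding | MDC with 0.408 s | Increase at 0.408 s | Increase at 0.289 s | Increase at 0.204 s |
|---|---|---|---|---|---|
| 0.5 s | 1.39 s | 1.79 s | +29% | +15% | +8% |
| 1 s | 2.77 s | 2.99 s | +8% | +4% | +2% |
| 2 s | 5.54 s | 5.66 s | +2% | +1% | +0.5% |
| 3 s | 8.32 s | 8.39 s | +1% | +0.5% | +0.2% |

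The last column follows from the formula; for example, at an SEM of 0.5 s, √(1 + 0.0417/0.25) − 1 = 8%. The increase is material only when the rest of the measurement error is small, at an SEM of about 0.5 s or less.

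**The case against.** The strongest reply is that this is an operational preference with little behind it. Several parts of that reply stand.

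- **The size is assumed.** No reading resolution appears in the protocol. The 0.41 s figure needs whole-second reading at both ends; careful reading halves it.
- **The MDC from rounding alone is not the inflation.** A reader might set 1.13 s against the normal time (1.13/10 = 11%, 1.13/7 = 16%) and conclude that the wristwatch raises the detectable change by that amount. The protocol does not support this. The 1.13 s is what the MDC would be if timing were the only source of error. Variances add, and the SEM is not given.
- **7 to 10 s is the normal time.** It is not presented as the time expected in people with Huntington's disease, and relative error falls in slower participants.
- **The link to the sub-study is an inference.** Section 10.1.9 names no device, and Section 5.4.7 says each sub-study will have its own protocol and procedures.
- **Other safeguards exist.** Section 5.1 provides training, certification and manuals, and Section 7.4 provides operating procedures and on-site checks. The device could be fixed there. Mixed devices are a possibility that the text allows, not a stated plan.
- **No stated result depends on it.** Section 6.2 is descriptive. Rounding to the nearest unit adds variance and not bias, in a cohort meant to be large.

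Two things limit this reply. The manuals are not part of the document, and whatever they say, Section 5.3.3.1 still permits the wristwatch. Nor is the error free of bias under every reading habit: if the test starts on a tick and only completed seconds are counted, the recorded time is on average 0.5 s too short.

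**Conclusion.** The point holds as a cheap improvement of low severity. Section 5.3.3.1 expressly allows a coarse instrument beside a fine one for a short test, and nothing else in the protocol withdraws that option or asks for one device throughout.

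On the assumption that the second hand is read at both ends to between a half and a whole second, rounding adds an SD of about 0.20 to 0.41 s per test, against about 0.03 s for a stopwatch recorded to 0.1 s. The direction of the effect on an MDC is certain; its size is not. At the upper end of the assumed rounding it runs from about +29% at an SEM of 0.5 s to +2% at 2 s, and it applies to the physiotherapy sub-study only if the same timing rule is used there.

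A reader might also infer that the study's sample size or power is compromised. It is not: no such figure, and no stated endpoint, rests on TUG precision.

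**What to change.** In Section 5.3.3.1, delete the wristwatch option and require a stopwatch, with the time recorded to 0.1 s, at every visit and every site. State the same rule for the TUG in Section 10.1.9 or in that sub-study's own protocol, and match it in the administration manual. The cost is one stopwatch per site and a sentence in each document. There is no added burden on participants and no change to the analysis.

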#### *5.3.3.2 30 Second Chair Stand Test*

The 30 second chair stand test provides a measurement of a person's lower body (particularly legs) strength. This is associated with the ability to perform lifestyle tasks such as climbing stairs, getting in and out of a vehicle or bath. The following instructions are provided to the participant:

1. Sit in the middle of the chair.
2. Place your hands on the opposite shoulder crossed at the wrists.
3. Keep your feet flat on the floor.
4. Keep your back straight.
5. On the signal to begin rise to a full stand position and then sit back down again.
6. Repeat this for 30 seconds.

Count the number of times the client comes to full standing position in 30 seconds. If the participant is over halfway to a standing position when 30 seconds have elapsed count it as a stand.

### **5.3.4 Quality of Life Assessments**

#### *5.3.4.1 Short Form Health Survey-12*

The Short Form Health Survey-12 (SF-12) contains 12 items that measure each of the eight concepts included in the SF-36 [45]. The SF-12 is extensively used in large

population health surveys as a brief, reliable measure of overall health status. The 1-week recall version will be used.

#### *5.3.4.2 Caregivers Quality of Life Questionnaire*

The Caregivers Quality of Life Questionnaire was developed as part of the REGISTRY study. This administered instrument that measures caregiver reactions, including perception and emotional feeling with regards to care giving. This general caregiver instrument provides direct evidence of impact on caregiver quality of life.

### **5.3.5 Health Economic Assessments**

#### *5.3.5.1 Client Services Receipt Inventory (CSRI)*

The Client Services Receipt Inventory (CSRI) questionnaire provides information on service utilization by collecting retrospective information on service related issues. It is an established tool and has been used in a range of research studies including mental health outreach services, community nursing services and community care of older people and people with challenging behavior [46]. The questionnaire schedule is designed for interviewer/researcher administration with the person receiving the services assisted by their main caregiver as required.

#### *5.3.5.2 Work Productivity and Activity Impairment-Specific Health Problem Questionnaire*

The Work Productivity and Activity Impairment-Specific Health Problem Questionnaire (WPAI-SHP) is a six-item questionnaire that measures effect of specific health problems on number of hours worked and the number of hours missed from work [47]. It also measures the effect of disease on productivity and regular activities. Decreases in values on each part indicate improvement. The sum of work time missed and impairment at work yields the overall work impairment (productivity loss) score; scores are expressed as percentage of impairment and/or productivity loss, with higher scores indicating greater impairment.

## **5.4 Optional Assessments**

Participating sites and individuals may choose to contribute these data elements. It requires that the participant provide specific consent to participate in these assessments.

### **5.4.1 Family History Questionnaire (FHQ)**

Participants who consent to this optional component will be asked to volunteer data covering 4 generations [i.e. information on their siblings and (if applicable) on their

spouse(s), data on their parents and the parental siblings (i.e., aunts and uncles) on the affected side of the family, data on their grandparents (i.e., the parents of their HD affected parent), and (if applicable) data on their children as well as on the offspring of their siblings (i.e., nieces and nephews)]. The purpose of the FHQ is (1) to render linked biosamples or data sets identifiable while protecting the privacy of all donors, (2) to obtain a family tree as an important part of standard medical care and (3) to provide a basis for studying the heritability of phenotypical traits in HD families as well as the intergenerational stability of the expansion mutation.

Participants and investigators will be asked to provide the following information on each person within the family tree:

- Gender
- Year of birth
- Vital status: if deceased, year and cause of death
- HD status (manifest/pre-manifest carrier/not a carrier & degree of certainty of the status designation)
- Availability of local DNA samples

No identifying information will be collected. From these data a family tree will be generated using appropriate software. Within this family tree, the symbols representing those members of the family who consented to participate in Enroll-HD will be annotated with their participant IDs; family members who did not consent to participate in Enroll-HD will be represented with symbols without an annotated participant ID.

#### **5.4.2 Biospecimens**

For participants who consent to donation of biosamples, up to 40 ml of blood will be collected at each annual visit for storage in a central biospecimen repository (BioRep). Specimens will be de-identified for storage and the central repository will have no access to identifying data. Participants may opt to participate at only the baseline visit or at any of the subsequent annual follow up visits. The banked blood will be used to generate lymphoblastoid cell lines, to extract DNA and cryopreserve lymphocytes.

A 10 ml yellow top ACD tube will be used for lymphoblastoid cell line creation and appropriate testing for viability and contamination. A second 10 ml yellow top ACD tube will be used for lymphocyte isolation and cryopreservation.

At specific sites with required specimen processing capabilities and proper training, plasma separation will be performed. In brief, blood will be drawn in a 9.5 ml EDTA tubes and centrifuged in a refrigerated within 30 minutes of blood draw. Plasma is

aliquotted into sterile cryotubes and placed in a -80°C freezer and subsequently shipped on dry ice using an overnight courier service. Shipping labels and detailed packaging instruction will be provided by the central biospecimen repository.

#### **5.4.3 Future Contact Regarding Research Studies**

Participants 18 years of age or older will be given the option of allowing the site research staff to maintain their name and contact information so that the site research staff may contact them regarding future participation in HD studies. This information will be kept confidential and will be stored at the site, separate from the Enroll-HD study database.

#### **5.4.4 Discussion of Post-Mortem Donation of Biological Materials**

As part of the informed consent process, participants will be alerted to the option of donating post-mortem tissues as part of Enroll-HD; as a first step, participants will be asked for permission to be approached to discuss the local options for post mortem donation of biological materials for research; the procedures for the collection and banking of post-mortem tissues will vary in compliance with the applicable regional regulations and will be presented in a separate, regional document.

#### **5.4.5 Transfer of Data from Other HD Studies and Trials**

HD is a slowly progressive, lifelong disease. Assessments of HD patients have been systematically collected using standard tools (e.g., UHDRS) in the course of their normal clinical visits or during previous or ongoing HD-related clinical studies or trials. In order to allow the HD research community to have access to these systematically collected clinical data recorded prior to Enroll-HD participants will be asked to provide permission for incorporation of a copy of clinical and laboratory data collected from them prior to the date of enrollment in Enroll-HD for integration within the Enroll-HD study database.

The collection of retrospective data will significantly enrich the clinical data available on this HD cohort. The combination of retrospective and prospective clinical data will provide a unique resource compiling all clinical data on a given participant in chronological order. These data can be used to understand more about an individual's trajectory for each parameter over the natural course of HD ('run-in data') and will help to quantify trial participation effects at the level of individual participants and individual raters. Consent to providing these data implies no additional burden on the participant.

#### **5.4.6 Transfer of Biospecimens from Other HD Studies and Trials**

For similar reasons participants will be asked to provide permission for transfer of biospecimens collected as part of other HD (previous or ongoing) studies and trials to the Enroll-HD biospecimen repository.

#### **5.4.7 Participation in Sub-Studies**

Apart from the study procedures associated with the main protocol of the Enroll-HD study, sub-studies involving a subpopulation of the Enroll-HD participants may be conducted under the Enroll-HD study umbrella. The purpose of these sub-studies is to provide a mechanism for establishing and validating novel assessment tools or assessment procedures by gathering data in specific HD populations and/or control populations and involves an iterative process of testing novel assessments, refining them and re-testing revised assessments.

Participation in sub-studies is optional: participants must first consent to be approached to participate in sub-studies generally and then volunteer for (i.e., consent) to participate in specific studies on a case-by-case basis. Sub-studies will only be implemented if the participant consents to this optional component and if the burden of the study visit assessments does not exceed 2.5 hours. By definition, assessments for sub-studies are noninvasive and imply limited burden on the participant.

These sub-studies are intended to better inform about specific and/or rare clinical phenotypes not presently captured in the established standardized assessments. Validation of assessment tools implies exploring the clinical metrics of the tool as well as inter-rater reliability. A systematic analysis of each item of the assessment tools used will allow the development of improved, more mature assessment tools. In a first pass, cross-sectional data will be gathered, and in a second pass, data gathering will extend to longitudinal data to look at the rate of changes in the various assessments.

A brief description of the currently proposed sub-studies is listed below and outlines are provided in the appendices. Each sub-study will have a separate protocol that details study procedures, standard operating procedures for study coordination, and a data analysis plan. Ethical review for sub-study protocols will be performed concurrently with the main Enroll-HD study protocol. Informed consent for the sub-studies will be obtained within the informed consent forms for the main Enroll-HD study.

New sub-studies may be proposed by qualified researchers and will need to be reviewed and approved by the Enroll-HD Steering Committee and will be implemented only after obtaining appropriate IRB/EC approvals.

Enroll-HD Sub-studies (see Appendix 1 for detailed descriptions):

- a. Pre-motor manifest HD - The objective of this sub study is to further validate clinical outcome measures to detect and track alterations in prodromal stages of HD. It will include participants with pre-motor manifest HD and will test a battery

- of assessments, developed in other HD studies including PREDICT-HD [48], TRACK-HD [49], and FurST-pHD and, to establish and evaluate a battery of quantitative motor, cognitive, oculo-motor, functional and behavioral domains..
- b. Advanced stage HD - The objective of this sub-study is to validate the “Advanced-stage UHDRS” for use in clinical and research practices. It will include participants with a UHDRS ‘99 Total Functional Capacity Score of  $\leq 5$ . The 4 components of the Advanced-HD scale (motor function, somatic domain, cognitive assessment, behavioral assessment) will be compared with the standard UHDRS ‘99 scale to assess progression of disease at one year.
  - c. Juvenile-onset HD - The objective of this sub-study is to develop and validate new scales and/or modify existing scales for outcomes of interest in Juvenile-onset HD. It will include participants with motor onset HD aged  $\leq 20$  years. Rasch analysis will be used to assess performance and to refine the UHDRS-JD rating scales. Semi-structured interviews and diaries will be used to collect data to inform the development of additional scales.
  - d. Frontal behaviors (FrSBE, Irritability and Apathy) - The objective of this sub-study is to validate existing measures of frontal behaviors in a HD population and develop sub-scales as outcome measures for trials. This sub-study will include confirmed HD gene mutation carriers who are  $\geq 18$  years of age. Data will be collected to understand the nature and course of frontal-type behaviors in HD and to identify scales that can be used as clinical outcome measures in interventional trials.
  - e. Linguistic Abilities - The objective of this sub-study is to characterize language impairment and assess syntactic abilities. It will include participants in the early stages HD. Syntactic abilities will be assessed using the Sentence Picture Matching Task with longitudinal data collection over a 1-year period.
  - f. Validation of the Montreal Cognitive Assessment (MoCA) - The aim of this sub-study is to validate the Montreal Cognitive Assessment. It will include participants at all stages of HD. A semi-randomized design will be used to assess cross-sectional and longitudinal sensitivity of this measure and to examine its utility in detecting and tracking global cognitive change.
  - g. Tapping - The objective of this study is to validate a finger/hand-tapping task as a measure of cognitive change. It will include participants at all stages of HD. All currently used tapping tasks in HD will be systematically reviewed to facilitate choice of a task that measures motor speed, dexterity and psychomotor speed and is sensitive and reliable.
  - h. HD Quality of Life (HD QoL) - The aim of this sub-study is to develop and validate a patient-reported health-related quality of life questionnaire specific for HD. It will

include participants at all stages of HD. The psychometric properties of the HD QoL instrument will be tested.

- i. **Physiotherapy outcome measures** - The objective of this sub-study is to develop physiotherapy-related outcome measures for use in future interventional studies. It will include participants at all stages of HD. A range of physiotherapy-related assessments (6-Minute Walk Test, 10-Minute Walk Test, Timed “Up and Go”, Physical Performance Test, Rivermead Mobility Index, Barthel Index, Berg Balance Scale, Romberg and Sharpened Romberg Test, Performance Oriented Mobility Assessment, Four Square Step Test, International Physical Activity Questionnaire) will be examined for utility as potential outcome measures.
- j. **Lifestyle factors** - The objective of this sub-study is to examine prospectively the link between lifestyle factors, age at onset of Huntington’s disease and rate of progression.

